Secondary Objective: The secondary objective of this study is to examine which patterns of atrophy predict the best response to treatment. This will help improve the selection of specific treatments for individual patients in the future.

Aim 2: To investigate which patterns of atrophy are associated with greatest response to treatment (improvement in naming verbs) in individuals with PPA following A-tDCS+therapy vs. sham+therapy.

Hypothesis: People with more IFG damage tend to have more trouble with verbs, so we predict they are likely to show the most change in verb naming following A-tDCS+therapy. It is possible that this hypothesis is incorrect, and they will show the least benefit from A-tDCS due to atrophy in IFG. It may be that people with more atrophy in other areas are going to benefit the most from this intervention.

3. Background (briefly describe pre-clinical and clinical data, current experience with procedures, drug or device, and any other relevant information to justify the research)

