The aim of this proposed study is to study whether the combined benefits of training complex items (building sentences by training verbs and their thematic roles) and applying A-tDCS to left IFG to improve naming will result in significantly greater maintenance and generalization to untreated items and structures, compared to the same training with sham stimulation, in participants with PPA. This study also aims to investigate which patterns of atrophy in PPA are predictive of the best therapy outcomes, which will serve to improve the selection of specific treatments for individual patients in the future. Changes to functional communication skills will also be investigated.

4. Study Procedures

a. *Study design, including the sequence and timing of study procedures (distinguish research procedures from those that are part of routine care).*

Study Procedures Overview

Study design overview: Participants will take part in 2 intervention periods of 15 training sessions (3-5 per week), with either tDCS + language therapy or sham+ language therapy, separated by 2 months. A computer-delivered naming treatment will be coupled with the stimulation. The computer-delivered treatment task will be 45-minutes in total length, so that it will commence at the same time as the tDCS administration and continue for another 25-minutes after the tDCS has ceased. All sessions, with the exception of the optional MRI, may take place at the participant's home or at a Hopkins site. When assessments and intervention are administered at the participant's home a study team member will perform the study procedure at home.

Visit 1: During the first visit, participants will undergo screening assessments. This will include tDCS and MRI safety screening. If the participant passes the initial screening portion, informed consent will be obtained. Neurological examination will also be performed (see below).

Visit 2: Participants may be asked to get MRI scanning, pending funding. Until funding is obtained, we will use MRI scans obtained for clinical purposes within 3 months of enrollment.

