- 3) Not medically stable
- 4) Picture naming ability below 10%
- 5) Picture naming ability above 85%
- 5) Significant history of drug or alcohol abuse or psychiatric or neurologic problems affecting the brain (other than PPA)
- 6) Non-MRI compatible pacemaker, implanted ferrous metal, claustrophobia, or other MRI contraindication
- 7) Seizures during the previous 12 months
- 8) Uncorrected visual loss or hearing loss by self-report
- 9) Use of medications that substantially lower the seizure threshold (e.g., methylphenidate) or use of NMDA antagonists (e.g., memantine)
- 10) History of brain surgery or any metal in the head
- 11) Scalp sensitivity (per participant report).

6. Drugs/ Substances/ Devices

a. The rationale for choosing the drug and dose or for choosing the device to be used.

tDCS has been established as a valid and reliable tool for at least temporarily affecting brain and behavior with minimal risks. Stimulation will be delivered by a battery-driven constant current stimulator (Soterix device, or a comparable model). The stimulator is not connected to a mainline power source and cannot produce in excess of 4mA of current. We will use non-metallic, conductive rubber electrodes covered by

Date: 01/11/2019
Principal Investigator: [name]
Application Number: IRB00174879

saline-soaked sponges to minimize the potential for chemical reactions at the interface of the scalp or skin and the electrodes.

b. *Justification and safety information if FDA approved drugs will be administered for non-FDA approved indications or if doses or routes of administration or participant populations are changed.*
N/A

c. *Justification and safety information if non-FDA approved drugs without an IND will be administered.* N/A

7. Study Statistics

a. Primary outcome variable

The primary outcome variable will be trained verbs on the OANB (OANBtrained) (pre-treatment and 1-week post-testing). To assess change in naming ability, the primary outcome in this study, the OANB) will be administered.

b. Secondary outcome variables

We will evaluate the effect of tDCS versus sham on change in naming of untrained verbs and nouns, and determine which pattern of atrophy is associated with the best treatment outcome.

c. Statistical plan including sample size justification and interim data analysis

Statistical Analyses

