For Aim 1, Hypothesis 1a This hypothesis states that Anodal tDCS (A-tDCS) plus VNeST therapy (A-tDCS+therapy) will significantly improve word retrieval of trained transitive verbs (from baseline to 1 week and 8 weeks post treatment). In the proposed study each participant will either receive tDCS (T) in the first intervention period followed by sham (S) in the second period (order = TS), or they will receive sham in the first period followed by tDCS (order = ST). For each participant, i , we will measure the change in word retrieval on the OANBtrained due to real tDCS stimulation by subtracting word retrieval performance accuracy on the OANBtrained before tDCS stimulation from the testing period 1 week following tDCS stimulation ($\delta Y_{i,tDCS}$). The identical measure will be computed for sham stimulation ($\delta Y_{i,sham}$). The data will be analyzed ($order_i, \delta Y_{i,tDCS}, \delta Y_{i,sham}$) for participants $i = 1, \dots, n$. Three models will be evaluated: the model of tDCS vs. sham, the model that adds the period effect, and the model that adds the interaction (a carryover effect). The predictive accuracy of these 3 models will be compared using the leave-one-out cross-validation R^2 . The model that best fits the data (the model with the highest R^2) will then be used to estimate the effect of tDCS relative to sham. This procedure will be repeated to determine changes from baseline to a period 8 weeks after treatment conclusion.

Sample Size Determination

We expect to enroll at least 50 participants with PPA over five years, and expect 45-50 will complete the study. This sample size is based on data collected from a separate study, IRB protocol number NA_00078932, PI [name]. *The effect size for anodal tDCS stimulation was 0.6 for trained items and 1.5 for untrained items.* We determined the number of participants to study, in order for the analysis to have 80% power to detect an effect size as low as 0.6. Allowing for 10% attrition, a sample size of 50 was chosen.

Missing Data

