We plan to minimize missing data by avoiding prolonged intervals between stimulations: 2 months may seem long with regard to the literature, but it is a reasonable length of time to be able to determine sustainability of any therapy. To minimize possible biases, analyses will be by intention to treat; any missing data will be addressed with the technique of multiple imputation (Rubin, 2004), generally recognized as best for handling missing data (Little et al., 2012).

Secondary Analyses

For Aim 1, Hypothesis 1b This hypothesis states that A-tDCS+therapy will generalize to other untreated verbs and nouns from baseline to 1 week and 8 weeks post treatment. The analyses will be identical to those described for Aim 1, Hypothesis 1a, except data from untreated verbs (OANBuntrained) and OANBnouns (untrained) will be used.

Aim 1, Hypothesis 1c Hypothesis 1c states that combined A-tDCS+therapy will result in greater improvement in functional communication skills compared to sham+therapy. Changes to functional communication skills resulting from A-tDCS+therapy vs. sham will be assessed using the ASHA FACS scale.

For Aim 2, Hypothesis 1: The proposed study aims to determine which patterns of baseline atrophy will predict the best response to A-tDCS plus a verb treatment using sentence building in individuals with PPA. People with more IFG damage tend to have more trouble with verbs, so we predict they are likely to show the most change in the primary outcome variable (OANBtrained verbs) with A-tDCS+therapy. It is possible that this hypothesis is incorrect, and they will show the least benefit from tDCS due to atrophy in IFG. It may be that people with more atrophy in other areas are going to benefit the most. Confirmation of either hypothesis will help select the best candidates for treatment. The area of peak atrophy (greatest difference between volume of each of the parcels on the JHU-MNI atlas in the participant compared to controls) will be identified for each participant. We will group participants by area of peak atrophy, and compare groups for each outcome variable, using Kruskal-Wallis one-way analysis of variance, for each outcome variable. As an exploratory analysis, we will also evaluate Spearman's correlations between the primary outcome variable and baseline volume in 5 regions of interest (areas affected in PPA: left IFG, left inferior temporal gyrus, left temporal pole, left superior temporal gyrus, and left supramarginal gyrus).

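### Aim 2 asks which atrophy patterns predict response to tDCS versus sham, but its planned tests contain no sham contrast, so a purely prognostic region could be reported as predicting tDCS benefit

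*Combined protocol and SAP*

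**What the plan says.** All places are in the combined protocol and SAP.

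- **Section 2, Secondary Objective, Aim 2** looks for the atrophy patterns linked to the greatest response "in individuals with PPA following A-tDCS+therapy vs. sham+therapy".
- **Section 7c, Secondary Analyses, Aim 2** predicts, for people with more IFG damage, that "they are likely to show the most change in the primary outcome variable (OANBtrained verbs) with A-tDCS+therapy". It allows that they may instead benefit least from tDCS, and adds: "Confirmation of either hypothesis will help select the best candidates for treatment".
- **The tests**, in the same place: "We will group participants by area of peak atrophy, and compare groups for each outcome variable, using Kruskal-Wallis one-way analysis of variance". As an exploratory addition, Spearman's "correlations between the primary outcome variable and baseline volume in 5 regions of interest".
- **The outcomes those tests use.** Section 2 (Aim 1) defines the primary outcome as change in trained-verb naming accuracy. Section 7a gives it as trained-verb naming before treatment and at 1 week after. Neither is a difference between tDCS and sham.
- **Section 7c, Aim 1, Hypothesis 1a** takes each participant's change around the tDCS period, then states "The identical measure will be computed for sham stimulation", and estimates the effect of tDCS relative to sham. Hypothesis 1b uses the same analysis, and Hypothesis 1c is also a comparison with sham. Nothing links Aim 2 to this contrast.
- **Looser wording of the aim** appears at the end of Section 3 ("which patterns of atrophy in PPA are predictive of the best therapy outcomes") and in Section 7b ("determine which pattern of atrophy is associated with the best treatment outcome").

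**The concern.** Asking who gains more from tDCS than from sham is a question about effect modification. Answering it requires the tDCS-minus-sham contrast to be compared across atrophy patterns. Comparing change under tDCS alone answers a different question: who changes more, for whatever reason, during a period in which tDCS and language therapy are both given.

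The two questions can easily diverge here. PPA is progressive, and atrophy pattern goes with variant and severity, so a region may predict decline, or response to language therapy, equally in both periods. Section 3 gives an example. A study in all three variants linked left temporal pole and left inferior temporal gyrus volume to naming of untrained nouns after therapy, without examining tDCS. Both regions are among the five in the Aim 2 correlations. That study concerned nouns and a different therapy, so it shows that a prognostic association is plausible but does not give its size in this trial.

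What is at stake is patient selection. A region that only marks slower decline, or better response to language therapy, could be presented as a marker for choosing who should receive tDCS.

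**Working it through.** **1. The plan's own figure.** The only sample-size figure is 50, and it concerns Aim 1. With effect size 0.6, 80% power and two-sided 0.05 (assumed; the plan does not state alpha), n = 2 × (1.960 + 0.842)² / 0.6² = 43.6, so 44, and 44 / 0.90 gives 49. The t-based version gives 45, and 45 / 0.90 = 50. The figure therefore reproduces if the two conditions are treated as independent. There is no corresponding figure for Aim 2. The calculations below use 45 participants, the lower end of the expected completers.

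**2. Why the contrast matters.** For participant i in atrophy group g, ignoring period:

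- change under tDCS: T = τ + p(g) + m(g) + u + e₁
- change under sham: S = p(g) + u + e₂

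Here τ is the average tDCS effect, p(g) the prognostic shift common to both conditions, m(g) the extra tDCS benefit in that group, and u the participant effect. A test on T responds to p(g) + m(g). In T − S = τ + m(g) + e₁ − e₂, the term p(g) cancels.

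**3. Size when the region is purely prognostic (m = 0).** Assumptions: normal change scores, one group shifted by 0.5, 0.8 or 1.0 within-group SD in both periods, equal groups unless stated, two-sided 0.05, no multiplicity correction. The documents give no prognostic strength and no number of groups. There were 10,000 simulated trials per Kruskal-Wallis setting and 20,000 per Spearman setting.

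| Test on the tDCS-period change | N | Significant |
|---|---|---|
| Kruskal-Wallis, 5 groups, shift 0.5 / 0.8 / 1.0 | 45 | 13% / 28% / 44% |
| Kruskal-Wallis, 3 groups, same shifts | 45 | 24% / 56% / 76% |
| Kruskal-Wallis, 5 groups, same shifts | 30 | 8% / 17% / 26% |
| Spearman, one region, prognostic correlation 0.2 / 0.3 / 0.4 | 45 | 24% / 48% / 75% |
| Spearman, same correlations | 30 | 17% / 33% / 55% |

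On T − S, the same settings give 3.8% to 4.7% (Kruskal-Wallis) and 5.0% to 5.4% (Spearman). The 30 is an assumed number of usable scans: Section 4a makes research MRI conditional on funding and otherwise relies on clinical scans.

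**4. If change is averaged over both conditions instead** (4,000 trials, N = 45, within-person correlation 0.5), the problem grows. Kruskal-Wallis is significant in 16% / 38% / 57% of trials with 5 groups and 31% / 69% / 87% with 3. Spearman at correlations 0.3 and 0.4 is significant in 59% and 85%.

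**5. Sensitivity to the groups** (4,000 trials, N = 45, tDCS-period change). With 10 groups of 4 to 5, Kruskal-Wallis is significant in 5% / 9% / 12%. With groups of 3, 6, 9, 12 and 15 and the shift in the smallest, it is 6% / 10% / 13%. The Spearman figures do not depend on grouping.

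**6. Power of the contrast.** Take a true extra tDCS benefit of 0.8 SD in one group. The SD of T − S is √(2(1 − r)), where r is the assumed within-person correlation of the two changes: 1.41, 1.18 and 1.00 at r = 0, 0.3 and 0.5.

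| Setting | Power on T − S at r = 0 / 0.3 / 0.5 |
|---|---|
| N = 45, 5 groups | 15% / 19% / 29% |
| N = 45, 3 groups | 31% / 41% / 54% |
| N = 30, 5 groups | 10% / 13% / 17% |

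On T alone with N = 45, power is about 28% (5 groups) and 55% (3 groups).

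**7. Order.** T − S also carries a period effect whose sign depends on sequence. With a 0.5 SD period effect, subtracting the mean difference of the participant's order group keeps false positives at 4.1% to 5.0%. At r = 0.3 and N = 45 it gives power of 20.3% against 17.6% uncentred (5 groups) and 39.4% against 33.7% (3 groups).

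**The case against.** The plan is silent rather than wrong. Kruskal-Wallis and Spearman can both be run on a tDCS-minus-sham difference, and a sympathetic reader can find that intention: Aim 2 is framed against sham, Section 7c speaks of benefit from tDCS, and both changes are computed for each participant. Conversely, the looser wording in Sections 3 and 7b makes gain under the combined package a legitimate question, and the selection sentence refers to treatment, not specifically to tDCS.

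The numbers can also be challenged. Grouping by the single most atrophied parcel of a whole atlas may give many small, unequal groups, for which the Kruskal-Wallis rates fall to 5% to 13%. The rate near 5% on the difference follows by construction from assuming an equal shift in both periods. The corrected analysis has little power. Aim 2 is secondary, and its regional correlations are already labelled exploratory.

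Most of this stands as qualification. It does not supply the missing contrast. Section 7b attaches the tDCS-versus-sham comparison to untrained verbs and nouns and lists the atrophy question separately. If the contrast is intended, it has to be written down. If package response is intended, the Section 2 aim and the selection statement need rewording. The lower Kruskal-Wallis rates leave the Spearman result as it is.

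**Conclusion.** The concern holds. The stated aim is a comparison with sham, the planned tests do not contain one, and nothing elsewhere provides it for Aim 2. Applied to the change under tDCS, which is how the hypothesis is worded, the tests cannot separate prognosis from added benefit of stimulation.

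The size is conditional on assumptions that the documents do not settle. For Kruskal-Wallis with 45 participants, a purely prognostic group is significant in 13% to 76% of trials across three or five equal groups and shifts of 0.5 to 1.0 SD, and in 5% to 13% with ten groups or with the unequal groups shown. For one region's Spearman test, the rate is 24% to 75% at prognostic correlations of 0.2 to 0.4. A wrong conclusion is therefore possible, not certain, and depends on which response the sponsor would actually use.

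The plan should be changed, because the result is meant to inform patient selection and the remedy is simple. The Aim 1 estimate of tDCS versus sham is not affected.

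**What to change.** Prespecify the Aim 2 response as each participant's δY under tDCS minus δY under sham, adjusted for order, for example by subtracting the mean difference of the participant's order group. Equivalently, test a region-by-condition interaction in a model that includes period. Use this response both in the peak-atrophy group comparison and in the five regional volume analyses.

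Report the association of atrophy with the sham-period change separately, labelled prognostic.

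If the intended question is gain under tDCS and therapy as a package, say so in Section 2 (Aim 2) and Section 7c, and do not describe the result as selecting candidates for tDCS.

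The change is to SAP wording only and needs no new data. The cost is power: at N = 45, about 15% to 29% with five groups and 31% to 54% with three for a 0.8 SD interaction, and about 10% to 17% with 30 scans in five groups. With ten small groups or the unequal groups above, it is about 7% (r = 0.3). The tDCS-only analysis has equal or higher power in these settings, but it cannot say what a positive result means. Aim 2 should therefore be presented as hypothesis-generating, with estimates and intervals.

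### The main Aim 2 test uses only the name of each participant's worst-affected region, although the hypothesis concerns the amount of IFG damage; the planned volume correlations fit better and should be promoted from exploratory

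*Combined protocol and SAP*

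**What the plan says.** Section 2 (Objectives, Aim 2) sets a general question: "To investigate which patterns of atrophy are associated with greatest response to treatment (improvement in naming verbs". The hypothesis there, repeated in Section 7c (Secondary Analyses, Aim 2), is graded: "People with more IFG damage tend to have more trouble with verbs, so we predict they are likely to show the most change". Both places allow the opposite direction, and both allow that atrophy elsewhere matters more.

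Section 7c then defines the predictor for the main test: "The area of peak atrophy (greatest difference between volume of each of the parcels on the JHU-MNI atlas in the participant compared to controls". Each participant thus receives one region name. The test follows: "We will group participants by area of peak atrophy, and compare groups for each outcome variable, using Kruskal-Wallis one-way analysis of variance". The number of parcels, a minimum group size, a pooling rule and follow-up contrasts are not given.

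The volumes themselves enter in one further sentence: "As an exploratory analysis, we will also evaluate Spearman's correlations between the primary outcome variable and baseline volume in 5 regions of interest". The regions are listed as "areas affected in PPA: left IFG, left inferior temporal gyrus, left temporal pole, left superior temporal gyrus, and left supramarginal gyrus".

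No sample size or power is stated for Aim 2. The Aim 1 calculation expects 45 to 50 completers.

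**The concern.** The hypothesis concerns how much IFG atrophy a person has. The main test sees only which parcel is worst. Someone with severe IFG atrophy and one slightly worse parcel elsewhere is counted outside the IFG group. Someone with mild atrophy whose IFG happens to be worst is counted inside it. Kruskal-Wallis also treats the groups as unordered, so a significant result says that some groups differ, but not that IFG is the region or which way the relation runs.

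Section 7c says that confirming either direction would help to select candidates for treatment. A null omnibus result could be misread as evidence that IFG atrophy does not matter, while the analysis that addresses the question directly has only exploratory standing. Promoting it after the data are seen would look selective.

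**Working it through.** **The plan's own figure.** The only sample size is for Aim 1: "in order for the analysis to have 80% power to detect an effect size as low as 0.6". A two-sample t-test at effect size 0.6, 80% power and two-sided alpha 0.05 (alpha is assumed; the plan gives none) needs 44.6, so 45 per group, and 45/0.90 = 50. This reproduces the stated 50 but says nothing about Aim 2. The plan has "expect 45-50 will complete the study"; I use n = 45. Fewer may have usable scans, because study MRI depends on funding and clinical scans are used until then (Section 4a, Visit 2).

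**Power of the correlation.** For Spearman, by Fisher z with variance 1.06/(n − 3), the standard error at n = 45 is √(1.06/42) = 0.159.
- At r = 0.4: atanh(0.4)/0.159 = 0.424/0.159 = 2.67, and Φ(2.67 − 1.96) = 76%.
- Smallest r detectable with 80% power, one test at 0.05: tanh[(1.960 + 0.842) × 0.159] = 0.42.
- The same with Bonferroni over five regions (alpha 0.01): tanh[(2.576 + 0.842) × 0.159] = 0.50.
- At n = 50 these two become 0.40 and 0.47.

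**Power of the peak-region test, by simulation.** Regional atrophy is normal with inter-region correlation 0.3. The label is the region with the greatest atrophy. Response = r × (standardised IFG atrophy) + √(1 − r²) × noise. Clustering is represented by three equally likely variants, each with its own region or regions shifted by 1.5 or 3 SD. All of this structure is assumed. There were 1,500 to 2,000 runs per cell.

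Kruskal-Wallis power at n = 45, r = 0.4:

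| Clustering | 3 labels | 5 | 10 | 20 | 50 |
|---|---|---|---|---|---|
| None | – | 12% | 5% | 1% | 0% |
| 1.5 SD | 29% | 20% | 11% | 4% | 1% |
| 3 SD | 47% | 34% | – | 30% | – |

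(Dashes: not run.) Spearman on IFG gave 75–80% in the same runs. A repeat run gave 0–11%, 1–20% and 24–46% for the three rows, against 72–78% for Spearman.

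**Why the power falls.**
- An indicator of IFG being the peak kept 41% (1.5 SD, three labels) to 67% (3 SD) of the variance in IFG atrophy.
- Without clustering, 20 parcels gave about 18 groups, of which about 5 were singletons; 50 parcels gave about 30 groups, about 19 of them singletons. With 3 SD clustering, 20 parcels gave only about 6 groups.
- Values below 5% partly reflect the chi-square approximation in tiny groups. Permutation p-values, without clustering, gave 13%, 10%, 6% and 7% for 5, 10, 20 and 50 parcels. Most of the loss therefore comes from the label.

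**If another region drives response.** At r = 0.4, Spearman on left IFG alone had 3–12% power. The five planned correlations, each at alpha 0.01, gave 51–58% and exceeded Kruskal-Wallis in every setting run.

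**The case against.** The strongest reply is that Aim 2 is wider than IFG. It asks which patterns matter and names other regions as a possibility, and an unordered comparison across regions does address that question, if coarsely. This stands. It also rules out a tempting remedy, left IFG volume as the only main test, which would leave the wider question almost untested if another region is responsible.

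The second reply is that the simulated response depends on IFG alone, which favours the IFG correlation, and that the Background describes three variants with distinct atrophy sites, so peak labels should cluster. This stands in part. With 3 SD clustering, three to six groups and r of 0.5 to 0.6, Kruskal-Wallis reached about 51–89%. A reader might infer that the main test has little chance of finding a real IFG relation. The documents do not support so general a statement, because they give no parcel count, degree of clustering or expected correlation. Even so, Spearman had more power in every IFG-driven setting, and at r of 0.4 or less Kruskal-Wallis never exceeded 47%.

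Third, a reader might infer that the plan throws away IFG volume. It does not: left IFG is among the five exploratory correlations. Only its rank in the analysis is at issue.

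Finally, the hypothesis says IFG without a side. Taking it as left rests on the stimulation target and the region list.

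**Conclusion.** The mismatch holds without any simulation. The main Aim 2 test uses neither the amount nor the direction of IFG atrophy, cannot name the region, and has no rule for small groups. Where response follows IFG atrophy, it is weaker than a correlation the plan already contains. The size of the loss is only illustrative: at n = 45 and r = 0.4, about 0–20% power with no or moderate clustering (five or more parcels) and 24–46% with strong clustering, against about 75%. These figures assume two-sided alpha 0.05, normal data and the region structure above.

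This is a cheap improvement to a secondary aim. It does not touch the primary analysis. Nor does it guarantee adequate power: a correlation of 0.3 would be detected only about half the time (50% at n = 45) even with the better test.

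**What to change.** Reword the Aim 2 paragraph of Section 7c before any data are analysed:

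1. **IFG hypothesis.** The main test is the two-sided Spearman correlation between baseline left IFG volume and the Aim 2 response, with that response variable named. It is two-sided because the plan allows either direction.
2. **Wider question.** The main analysis is the set of five planned regional correlations with the same response, adjusted for multiplicity, for example by Holm or Bonferroni. State in advance that left IFG is read unadjusted for item 1 and within the adjusted set for item 2.
3. **Peak-parcel Kruskal-Wallis.** Keep it as supportive or descriptive, with a small set of groups or a pooling rule fixed beforehand.

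No new scans, measures or participants are needed, because the five volumes are already planned. There are two costs. Regions outside the five are only described, so a relation confined to one of them would have no main test. The adjustment raises the smallest correlation detectable with 80% power at n = 45 from about 0.42 to about 0.50.
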